#### ***Role of Isomark***

Isomark will report to the investigators of the study site(s) all SAEs that are unexpected and associated with use of the Isomark Canary, or UADEs.

Isomark assumes responsibility for appropriate reporting of SAEs to regulatory agencies. Sites should follow their individual reporting guidelines to their local regulatory agencies.

The PI, the study independent medical monitor, and the sponsor will be the primary data and safety advisory group for the study.

The study will include interim review of actual and projected subject accrual rates, subject demographics, and a number and severity of AEs. The PI, the study independent medical monitor, and the sponsor will collaboratively determine actions of continuation, modification, or termination of the study.

## 10.0 Data Monitoring

The PI, the study independent medical monitor, and the sponsor will be the primary data and safety advisory group for the study.

The study will include interim review of actual and projected subject accrual rates, subject demographics, and a number and severity of AEs. The PI, the study independent medical monitor, and the sponsor will collaboratively

determine actions of continuation, modification, or termination of the study. Refer to Isomark's Data Management Plan (DMP) for additional details.

### **10.1 Endpoint assessment, adjudication**

An endpoint assessment and adjudication committee (EAC) of three clinicians will review study recorded infections and sepsis diagnoses to determine accuracy of protocol specified criteria and to determine and develop criteria for BDV clinical use. None of the EAC will have been directly involved with care of the patient who is a study subject. Information to be reviewed may include clinical laboratory, pathology or imaging data, autopsy reports, physical descriptions, and other data deemed relevant. The EAC will be blinded to BDVs, and will not know if BDV changed for a particular subject. EAC members will receive de-identified study records, and will not receive study subject PHI.

Each EAC member will independently review study subjects' data to determine their infection status. The decision of the subject's infection status will be recorded in the EAC Infection Status case report form. The EAC's charter will outline their role as an EAC member, guidelines for completing the Infection Status case report form, and definitions that should be utilized and followed for the purposes of this study protocol.

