### ICU/IMC Study Days:

- Assess for capacity to consent
- Breath samples
- Blood sample collection
- Vital signs
- Urine output
- Record standard of care lab values (e.g. CBC, bacterial cultures, PCT,etc)
- Diagnostic imaging
- Catheters, drains, lines
- Bedside procedures, interventions
- Surgical procedures
- Medications
- Nutrition status, support
- Mechanical ventilatory support
- Duration of ICU/hospital stay
- Medical history/diagnoses
- Adverse events

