- Blood samples and the original copies of the corresponding blood sample collection records will be placed in an Isomark-provided container and shipped to Isomark's contracted reference lab via an Isomark-approved carrier. The blood samples are processed by the reference lab and the results are sent to the sites, and will need to be entered into the EDC by the site staff. After the results have been successfully received, the lab will dispose of any remaining blood samples.
- Each time breath samples are received, Isomark personnel will check the samples for complete label information and compare the samples to the EDC, noting any anomaly. Isomark personnel will then update the corresponding sample check-in record with sample arrival, inspection, and condition information, dating and initialing where instructed.
- At the beginning of each day on which samples are analyzed, the sample analysis technician will ensure the Canary is within calibration specifications by analyzing a standard sample of known isotopic composition and initial the sample analysis record.
- Breath samples are to be analyzed within 21 days of the time of collection. Isomark personnel will note the time and date of sample analysis on the sample analysis record and initial.
- Data will be recorded on the sample analysis record and initialed by the technician.
- After breath sample analysis is complete, the technician will ensure the remaining breath is exhausted (by expelling all remaining sample from the sample bag) or destroyed (by disposal as biomedical waste in the case of plasma samples) and will initial the sample analysis record.
- After breath analysis is complete, Isomark personnel will enter the results into the EDC.

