### Hypotheses

#### Co-Primary Endpoint 1

1. Null hypothesis: BDV sensitivity is more than 10% worse than PCT sensitivity for progression to severe sepsis and septic shock in critically ill adult ICU subjects
2. Alternative hypothesis: BDV sensitivity is less than 10% worse than PCT sensitivity for progression to severe sepsis and septic shock in critically ill adult ICU subjects

#### Co-Primary Endpoint 2

1. Null hypothesis: BDV specificity is more than 10% worse than PCT specificity for those not progressing to severe sepsis and septic shock in critically ill adult ICU subjects
2. Alternative hypothesis: BDV specificity is less than 10% worse than PCT specificity for those not progressing to severe sepsis and septic shock in critically ill adult ICU subjects.

#### Secondary Endpoint 1

1. Null hypothesis: the variability of BDV in critically ill adult ICU subjects does not change after clinical diagnosis of progression to severe sepsis and septic shock.
2. Alternative hypothesis: the variability of BDV in critically ill adult ICU subjects increases after clinical diagnosis of progression to severe sepsis and septic shock.

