## **6. Analysis Sets/Populations/Subgroups**

The first task is to demonstrate that there is a positive signal associated with the Canary test using the subject as their own control.

A per protocol analysis will be performed following EAC event reconciliation and subsequent database lock. The EAC will determine diagnostic truth by documenting severe sepsis or septic shock events as well as the onset and resolution dates.

Infection documentation will be reviewed by the EAC committee based on best clinical practices, using four categories:

- No suspicion of infection
- Inconclusive evidence of infection
- High suspicion of infection
- Overt infection

For sensitivity and specificity, non-inferiority testing will be performed to rule out a -10% disadvantage according to a one-sided 97.5% lower confidence limit for the BDV – PCT

difference; exact McNemar paired comparison tests will be performed to test BDV non-inferiority relative to PCT. Both endpoints must achieve statistical significance in order to achieve study success.

PPV and NPV will be computed as observed and for a range of possible infection prevalence (10%, 20%, 30%, and 40%). Results will be analyzed in the same manner as sensitivity and specificity.

BDV variations will be assessed using a two-sample t-test to compare the averaged (across time points) BDV between subjects who are diagnosed with a severe sepsis and sepsis shock vs. no severe sepsis or sepsis shock. Also a linear mixed effects model with subject specific random effects will be used to compare BDV measurements between the two diagnostic groups. This model will be also used to estimate the intra- and inter-subject variability of the BDV measurements. A paired t-test will be used to compare the BDV measurements prior to and after a diagnosis of infection or sepsis.

The definition of a positive BDV will be based on a 72-hour window without advance knowledge of the diagnosis. In the absence of clinical details supporting PCT operating characteristics (sensitivity, specificity), two PCT thresholds (0.5 and 2.0) will be evaluated but the 0.5 threshold is deemed to be primary for BDV comparison.

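### The adjudication committee is blinded to BDV but nothing blinds it to PCT, the comparator in both SAP co-primary tests, so the reference diagnosis can incorporate PCT and bias the comparison against BDV

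*Protocol*

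**What the plan says.** **Who sets truth.** SAP section 6: "The EAC will determine diagnostic truth by documenting severe sepsis or septic shock events as well as the onset and resolution dates".

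**What is tested on it.** The first co-primary null hypothesis (SAP section 5, Hypotheses) is that "BDV sensitivity is more than 10% worse than PCT sensitivity for progression to severe sepsis and septic shock". The second is the same statement for specificity. SAP section 6 requires both to succeed.

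**What the EAC may see.** Protocol 10.1: "Information to be reviewed may include clinical laboratory, pathology or imaging data, autopsy reports, physical descriptions, and other data deemed relevant". The only blinding is to BDV: "The EAC will be blinded to BDVs, and will not know if BDV changed for a particular subject". The SAP adds no blinding statement of its own. Adjudication guidelines and definitions are left to an EAC charter that is not among the documents.

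**Where PCT sits.** There are two sources.
- Standard of care: Protocol 11.6 lists, for ICU/IMC days, "Record standard of care lab values (e.g. CBC, bacterial cultures, PCT,etc", with similar entries for the two follow-up periods.
- Research samples: Protocol 5.7 keeps PCT and CRP results from clinical care providers and study team members until all data and sample collection is complete. Protocol 5.11 keeps laboratory results from the subject and the care team. Protocol 11.10 then says of the blood results that "the results are sent to the sites, and will need to be entered into the EDC by the site staff".

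**The concern.** In a paired accuracy comparison, neither test should help to define the disease on which both are scored. Here one test is withheld from the adjudicators and the other is not. An adjudicator who sees a low PCT is less likely to call an event, and one who sees a high PCT is more likely to. Either habit moves labels towards PCT. Apparent PCT sensitivity and specificity rise, and the BDV minus PCT difference falls on both co-primary endpoints.

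Two things are at stake. A device that meets its target could fail, because both tests must succeed. The accuracy estimates for both markers, and the predictive values that the SAP builds on them, would also be distorted.

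**Working it through.** **1. Reproduce the planned power.** Inputs from SAP Tables 1 and 2: n = 97 pairs, expected difference d = 0.10, discordant proportion η = 0.40, margin 0.10, one-sided 2.5%. Wald approximation for a paired difference:

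Power = Φ( (d + 0.10)/√((η − d²)/n) − 1.96 )

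√((0.40 − 0.01)/97) = 0.0634; 0.20/0.0634 = 3.154; Φ(1.194) = 88.4%. The SAP's simulations give 89% (sensitivity) and 87% (specificity). The non-inferiority columns (d = 0.015, η = 0.315) give 52.3%, against 51% and 52%. The planned figures are not in dispute.

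**2. Recover the cells.** d = 0.10 and η = 0.40 give BDV+/PCT− = 0.25 and BDV−/PCT+ = 0.15 among the diseased. With both positive at 0.60, BDV sensitivity is 85% and PCT 75%.

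**3. Illustration: a share r of the BDV+/PCT− diseased cases is called non-diseased because PCT was low.** The value of r is an assumption; the documents give none.

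d = (0.25(1 − r) − 0.15)/(1 − 0.25r); η = (0.25(1 − r) + 0.15)/(1 − 0.25r); n = 97(1 − 0.25r)

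| r | Subjects moved (97 × 0.25r) | n | Apparent BDV / PCT sensitivity | d (points) | Power |
|---|---|---|---|---|---|
| 0 | 0 | 97 | 85.0% / 75.0% | 10.0 | 88% |
| 10% | 2.4 | 94.6 | 84.6% / 76.9% | 7.7 | 80% |
| 20% | 4.9 | 92.2 | 84.2% / 78.9% | 5.3 | 68% |
| 30% | 7.3 | 89.7 | 83.8% / 81.1% | 2.7 | 53% |

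**4. The same subjects also affect specificity.** Once called non-diseased, they count as BDV false positives and PCT true negatives. With m subjects moved into the 97 non-diseased, d = (9.7 − m)/(97 + m) and η = (38.8 + m)/(97 + m), with n = 97 + m. For m = 2.4, 4.9 and 7.3 the difference is 7.3, 4.8 and 2.3 points, and power is 77%, 63% and 47%.

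**5. A second illustration: labels drift both ways.** Suppose the label follows PCT instead of truth in a fraction f of 194 subjects split 50:50, as the SAP assumes. Among the non-diseased, Table 2 gives BDV+/PCT− 0.15 and BDV−/PCT+ 0.25. Then d = (0.05 − 0.25f)/(0.5 + 0.05f) for sensitivity and (0.05 − 0.25f)/(0.5 − 0.05f) for specificity.
- f = 5%: 7.5 points on both; power 79% and 78%.
- f = 10%: 5.0 and 5.1 points; power 66% and 64%.
- f = 20%: zero on both; power 36% and 33%.

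**6. Direction at the margin.** Reverse the cells in step 3 so that BDV is truly 10 points worse (0.15 and 0.25). At r = 10%, d = (0.135 − 0.25)/(1 − 0.015) = −11.7 points. The apparent difference moves further from non-inferiority.

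**The case against.** The strongest reply is that the gap is one of silence. Protocol 10.1 says what the EAC may review, not what it will; the charter could exclude PCT. The SIRS criteria in Protocol 6.1 do not use PCT. Research PCT is restricted by Protocol 5.7 and 5.11, access to the data system is role-based (Protocol 11.1), and the EAC receives de-identified records. Any adjudication done while collection is still running would precede release of the research results. This stands as far as it goes. However, the restrictions do not name the EAC, do not cover standard-of-care PCT, and for care providers and study team members lapse under 5.7 when collection ends.

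Four stronger readings are tempting and are not supported:
- *PCT is available to adjudicators for every subject.* The Schedule of Assessments marks standard-of-care laboratory work as done if clinically indicated, Protocol 11.6 gives PCT only as an example, and Protocol 1.0 calls it not commonly available in US clinical laboratories. Exposure is partial and may differ by site.
- *The power figures estimate the loss.* They rest on assumed relabelling rates and only show sensitivity to them.
- *The EAC has an impossible remit, because it is also asked "to determine and develop criteria for BDV clinical use" while blinded to BDV.* Doing that work after blinded adjudication is a natural reading.
- *CRP must be blinded for the same reason.* CRP is in neither co-primary test.

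**Conclusion.** The point holds as a gap in the plan: followed as written, it permits one-sided incorporation of the comparator into the reference diagnosis. Nothing shows that this will happen, and its size cannot be derived from the documents. On the SAP's planning inputs, moving two or three of 97 cases takes sensitivity power from 88% to about 80%, and moving about seven takes it to 53%. These figures assume that PCT was visible and decisive in those cases.

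A reader might infer that the gap threatens a false claim of success. Under the relabelling examined it does the opposite: the bias runs against BDV, including at the margin. The cost is lost power and distorted accuracy estimates. This makes the change a worthwhile, inexpensive improvement and not a threat to the Type I error rate.

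**What to change.** In Protocol 10.1 and the EAC charter:
1. State that the EAC is blinded to PCT, both research and standard-of-care, as well as to BDV.
2. Exclude PCT from the adjudication criteria.
3. Redact PCT values from adjudication packets.
4. Keep research PCT results out of any record the EAC can reach until adjudication is locked.

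In the SAP, report how many adjudicated subjects had a standard-of-care PCT, and repeat both co-primary analyses without them as a sensitivity analysis.

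The cost is wording, redaction of one analyte and an access rule. Adjudicators lose one clinical marker. Redaction does not remove PCT influence already carried in the treating team's recorded diagnoses, which is why the sensitivity analysis is needed. That analysis will have fewer pairs, and it drops subjects in whom clinicians chose to order PCT, so it should be read as a check on direction. The change must be made before adjudication starts, since labels assigned with PCT in view cannot be made blind afterwards.

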## **11.0 Administrative requirements**

### **11.1 Data record and management**

Study team will be provided with secure access to and training using Overture Electronic Data Capture (EDC) System to assure accurate, error free data acquisition for each study subject. A specific data set will be recorded and completed for each study subject. The PI is responsible to ensure the accuracy, completeness, and timeliness of the data recorded. The PI or designated representative shall complete the data set using Overture within 2 calendar weeks after the information is available and the subject has completed the study.

Overture is a clinical trial database software that will provide the electronic data management system for this study to acquire, store, edit, manage, and export study data for analysis.

The study team will manage study data with Overture. Access to Overture is restricted to those who have been provided access by the database administrators. User access requires supervisor approval, completion of HIPAA and Human Subjects Protection training, and completion of role based training in Overture. Users' access is limited to protocols for which they have responsibility for protocol, subject, or data management. Within those protocols, the ability to view and modify data is restricted based on the user's location and role in the conduct of the research project (e.g. sponsor staff does not have the privilege to view identifiable subject information).

The technical components of Overture are managed by Isomark administrative staff. Information Technology team (for server maintenance, software upgrades, etc.), security and software support is provided by Isomark LLC (sponsor).

All communication between the users and Overture occurs via a secure internet browser with individually assigned user controls. This ensures that data passing between the client and Overture is protected from unauthorized data access. Overture fully supports compliance with 21 CFR Part 11.

Overture is hosted on a physically and logically secured COTS (commercial off the shelf) server running Microsoft SQL Server software. Data is exported from Overture with indirect identifiers (i.e. with subject number) for statistical and data monitoring purposes in an MS Excel, SAS, or similar analysis program format. At study completion, all data will be exported and data within Overture will be eliminated.

## 11.2 Ethical considerations

This study is to be conducted according to US and international standards of Good Clinical Practice (FDA Title 21 part 812 and International Conference on Harmonization guidelines), applicable government regulations, and institutional research policies and procedures.

This protocol and any amendments will be submitted to a properly constituted independent Institutional Review Board (IRB), in agreement with local legal prescriptions, for formal approval of the study conduct. The decision of the IRB concerning the conduct of the study will be made in writing to the investigator, and a copy of this decision will be provided to the sponsor before commencement of this study.

All types of reportable events (non-compliance, UADEs, SAEs) will be recorded and reported following IRB policies.

All subjects for this study will be given a consent form describing this study and providing sufficient information for subjects to make an informed decision about their participation in this study. This consent form will be submitted with the protocol for review and approval by the governing IRB for the study. The formal consent of a subject, using the IRB approved consent form, must be obtained before that subject undergoes any study procedure. The consent form must be signed by the subject and the investigator designated research professional obtaining the consent.

## 11.3 Subject confidentiality

Information about study subjects will be kept confidential and managed according to the requirements of the Health Insurance Portability and Accountability Act of 1996 (HIPAA). All subjects will sign an informed consent document and HIPAA authorization that names specific privacy and confidentiality rights. Study data will be maintained per Federal and State data policies.

Protected Health Information (PHI) may not be disclosed to the sponsor, Isomark, LLC. To protect subject privacy, data provided to Isomark will be de-identified with the exception of dates and times. Please refer to the informed consent form for this study for further details specifying use of PHI in this study.

## 11.4 Data quality and management

Monitoring of this study will be conducted by the sponsor and independent clinical monitors. Study monitoring activities will include: (1) a site qualification visit; (2) a study startup meeting, referred to as the Site Initiation Visit; (3) interim monitoring visits to directly review study materials (regulatory files, consent forms, case report forms, device accountability records); (4) a final study close out visit. Monitoring plan details are outlined in Isomark's Clinical Monitoring Plan.

The research personnel based at the study site, assigned clinical study monitors and Isomark, LLC will complete Site Initiation Visit procedures after IRB approval and before enrollment of any subjects in the study. The Site Initiation Visit will include a summary of all training, monitoring activities and expectations during the study.

Interim monitoring activities will utilize the risk based monitoring approach described in the FDA draft guidance document. Following this approach, data directly supporting the primary analysis of this study will be 100% monitored and 25% of the remaining data for all subjects will be reviewed. Data from additional subjects may be reviewed if significant deficiencies are identified.

## 11.5 Source documents

Source documents will contain source data for the study. Specified source data will be recorded in the Overture EDC by manual transcription or other automated method that may become available. The study subject data set specifies the data to be recorded for each subject.

## 11.6 Subject study data set

If a datum is not applicable to the individual subject case, then this will be documented as 'N/A'.

### Baseline Data:

- Informed consent obtained
  - NOTE: The study team will assess the capacity of each potential subject to consent daily and at every study encounter until capacity for consent is regained or until the subject is discharged from the study hospital.
- Demographic data
  - NOTE: The study team will verify SOC pregnancy test is negative for women of childbearing potential.
- Infections Signs and Symptoms (SIRS and MEWS data)
- Medical history and current clinical diagnoses
- Medical record abstraction, including but not limited to:
  - smoking history
  - vital signs
  - clinical laboratory analyses
  - concomitant medications

### ICU/IMC Study Days:

- Assess for capacity to consent
- Breath samples
- Blood sample collection
- Vital signs
- Urine output
- Record standard of care lab values (e.g. CBC, bacterial cultures, PCT,etc)
- Diagnostic imaging
- Catheters, drains, lines
- Bedside procedures, interventions
- Surgical procedures
- Medications
- Nutrition status, support
- Mechanical ventilatory support
- Duration of ICU/hospital stay
- Medical history/diagnoses
- Adverse events

### Post ICU/IMC Study Days:

- Assess for capacity to consent
- Readmission information
- Vital signs
- Urine output

- Record standard of care lab values (e.g. CBC, bacterial cultures, PCT, etc)
- Diagnostic imaging
- Catheters, drains, lines
- Bedside procedures, interventions
- Surgical procedures
- Medications
- Nutrition status, support
- Mechanical ventilatory support
- Duration of ICU/hospital stay
- Medical history/diagnoses
- Adverse events

